4.5.2 Replacement of Subjects

Subjects will not be replaced.

4.5.3 Premature Closure of the Clinical Trial

If the 30-day complication rate (any stroke or death) of one or both treatment modalities exceeds 3% (with an 80% confidence interval), the Data Safety and Monitoring Board (DSMB, see chapter 0) can give a recommendation to the steering committee to stop the trial. If the complication rate exceeds 5%, the DSMB will recommend stopping the trial.

The trial can be prematurely closed or suspended by the Executive Committee in case of new data about the risk-benefit of one of the treatment regimes becomes available or if the DSMB recommends study closure. The Ethics Committee (EC) and the competent regulatory authorities must then be informed. Furthermore, the Ethics Committee(s) and competent regulatory authorities themselves may decide to stop or suspend the trial.

Should the trial be closed prematurely, all trial material must be returned to the Coordinating Clinical Centre (Department of Neurology, University of Heidelberg)

All involved investigators have to be informed immediately about a cessation/ suspension of the trial. The decision is binding to all trial centers and investigators.

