4 SELECTION OF SUBJECTS

4.1 Number of subjects

OLD: As calculated in section 9.1 'Sample Size Calculation', 3,640 subjects should be enrolled in the clinical trial, 540 to the BMT-Arm, 1,550 to the surgical and 1,550 to the stenting-group.

NEW: As calculated in section 9.1 'Sample Size Calculation', 1636 subjects should be enrolled in the group sequential clinical trial with one interim analysis, 818 patients per arm. This is the case for SPACE2a comparing CEA with BMT and for SPACE2b comparing CAS with BMT. Both trials would require a total of 3,272 patients.

Recruitment and treatment of subjects should be performed in around 100 trial centers. The minimum / maximum number of subjects per trial centre should be 10/200.

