9.4 Statistical methods

Biometric analysis will be defined in the statistical analysis plan which has to be authorized before closing the database by the biometrician, the sponsor, and the LKP.

OLD: Safety: The one-sided 97.5% confidence interval under H_0 for the difference of the event rates (rate in the CAS group – the rate in the CEA group) will be calculated. Non-inferiority is proven if the upper margin of this interval is less than 1.5%. This test has power of 90% if CAS shows a slight safety advantage compared to CEA (2.5% CAS versus 3% CEA). The power of the non-inferiority test is 80% in case of a slightly reduced risk in both procedures (CAS and CEA 2%).

Efficacy: In order to control the overall Type I error on the 5% level, a hierarchical testing procedure will be used. The first step of the procedure consists in a closed testing procedure for the difference between the three treatments. The tests are performed on a 5% level. If there are simultaneously significant differences between the pairs BMT and CEA as well as BMT and CAS on a 5% level, the hierarchical testing procedure enters step 2, otherwise there is no further statistical testing. Since superiority for CEA and CAS over BMT is not yet established in the studied population both tests need to be significant to allow the interpretation of step 2 in a clinically sensible way. Step 2 of the procedure consists in a non-inferiority test: The one-sided 97.5% confidence interval for the difference of the event rates (rate in the CAS group – the rate in the CEA group) will be calculated. Non-inferiority is proven if the upper margin of this interval is less than 2.5%.

In case of losses to follow up, the event rates and their standard errors will be calculated by Kaplan-Meier-techniques.

NEW:

Safety: If in the interim analysis the absolute rate of safety events (any stroke or death within 30 days after intervention) in the CEA-arm (for SPACE2a) or in the CAS-arm (for SPACE2b) with a confidence interval of 80% is higher than 3%, the DSMB can recommend stopping the trial. If the lower 80%-confidence-interval of the safety-event-rate is higher than 5%, the DSMB will recommend stopping the trial.

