9.5 Interim analyses

OLD: No interim analysis is planned with respect to the primary endpoint. An interim analysis of the safety data is planned after three years. This will not influence the sample size calculation because this is based on the efficacy endpoint. In addition the safety committee will check the safety regularly.

NEW: One interim analysis is planned with respect to the primary endpoint after five years. An interim analysis of the safety data is planned after three years. This will not influence the sample size calculation, because this is based on the efficacy endpoint. In addition the safety committee will check the safety regularly.

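### Sections 4.5.3 and 9.4 of the protocol set different triggers for the obligatory 5% stop recommendation by the DSMB

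*Protocol*

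**What the plan says.** Section 4.5.3 (Premature Closure of the Clinical Trial) has two steps for the 30-day rate of stroke or death. The DSMB may recommend stopping if the rate "exceeds 3% (with an 80% confidence interval"). The next sentence makes the recommendation obligatory: "If the complication rate exceeds 5%, the DSMB will recommend stopping the trial". It mentions no interval and no time point.

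Section 9.4 (Statistical methods, NEW, Safety) has the same two steps. The paragraph opens with "If in the interim analysis the absolute rate of safety events". The optional step applies if the rate "with a confidence interval of 80% is higher than 3%, the DSMB can recommend stopping the trial". The obligatory step reads: "If the lower 80%-confidence-interval of the safety-event-rate is higher than 5%, the DSMB will recommend stopping the trial".

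The protocol labels superseded text OLD and its replacement NEW. Section 4.5.3 carries neither label, and the 9.4 paragraph is labelled NEW, so both are in force.

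On timing, section 9.5 says: "An interim analysis of the safety data is planned after three years", and adds regular safety checks. It gives no number of patients for either. Section 4.1 plans "818 patients per arm" in each substudy. On who acts, section 4.5.3 says: "The trial can be prematurely closed or suspended by the Executive Committee".

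**The concern.** The two sections share the 5% threshold and the consequence, an obligatory recommendation. They differ in what is compared with 5%: the complication rate itself in 4.5.3, and its lower 80% confidence limit in 9.4. The lower limit always lies below the observed rate, so 9.4 needs more events before it obliges the DSMB to act. They also differ on timing, because 9.4 places the rule in the interim analysis and 4.5.3 sets no time.

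At stake is whether a given set of safety data binds the DSMB to recommend stopping or leaves it free to choose. An ethics committee relying on one section and a DSMB member relying on the other could disagree on that, and each would be following the protocol.

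**Working it through.** The protocol states no event count or trigger probability for the 5% rule, so there is no figure to reproduce. The check finds the number of events at which each wording takes effect.

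**Inputs from the protocol.** Threshold 5% (4.5.3 and 9.4); 80% confidence level (9.4); 818 patients per arm (4.1), which is the most an intervention arm can contribute.

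**Assumptions.** The number treated at the look is not given; 100, 200, 400 and 818 are used. The interval method is not given either. Exact (Clopper-Pearson) limits are used, with a lower tail of 10% (two-sided 80% interval) or 20% (one-sided 80% limit).

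**Formulas.** For x events in n treated patients:
- 4.5.3: smallest x with x/n > 0.05.
- 9.4: smallest x with L(x) > 0.05, where L(x) is the a-quantile of the Beta(x, n − x + 1) distribution and a = 0.10 or 0.20.

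| n (assumed) | 4.5.3 trigger | 9.4, one-sided 80% | 9.4, two-sided 80% |
|---|---|---|---|
| 100 | 6 (6.00%) | 8 (8.00%) | 9 (9.00%) |
| 200 | 11 (5.50%) | 14 (7.00%) | 15 (7.50%) |
| 400 | 21 (5.25%) | 25 (6.25%) | 27 (6.75%) |
| 818 | 41 (5.01%) | 47 (5.75%) | 50 (6.11%) |

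Example: 23 events in 400 patients is 23/400 = 5.75%, above 5%, so 4.5.3 obliges the recommendation. The exact lower limit is 4.30% (two-sided) or 4.74% (one-sided), both below 5%, so 9.4 does not.

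Other interval methods move the 9.4 trigger slightly. With Wilson and Wald limits included, the range is 7 to 9 events at n = 100, 13 to 15 at n = 200 and 47 to 50 at n = 818. No method tried brings it down to the 4.5.3 trigger.

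**Chance of triggering at a single look.** P(X ≥ k) with X binomial(n, p) and k from the table:

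| n | True rate p | 4.5.3 | 9.4, one-sided | 9.4, two-sided |
|---|---|---|---|---|
| 400 | 5% | 0.44 | 0.15 | 0.07 |
| 400 | 6% | 0.77 | 0.45 | 0.29 |
| 818 | 5% | 0.52 | 0.18 | 0.09 |
| 818 | 6% | 0.90 | 0.64 | 0.47 |

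**What the optional 3% rule does in the gap.** Both sections let the DSMB recommend stopping when the rate, with an 80% interval, exceeds 3%. Read as a lower limit above 3%, this is checked at the 4.5.3 trigger with the two-sided exact limit: 3.2% (6/100), 3.5% (11/200), 3.9% (21/400) and 4.1% (41/818). All exceed 3%. Throughout the gap the DSMB may therefore already recommend stopping under either section; the sections differ on whether it must.

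**The case against.** The strongest reply is that little turns on the difference. Neither section stops the trial: the DSMB recommends, and the Executive Committee can then close. With exact limits, the 3% rule already permits the recommendation wherever the two 5% rules disagree. This stands, and it limits the consequence. A reader might infer that the same data would stop the trial under one section and let randomisation continue under the other, or that 77% against 29 to 45% is a difference in the chance of stopping. The documents do not support that; these are chances that a recommendation becomes obligatory. One small exception to the reply: with a two-sided Wald interval at n = 100, the 3% rule needs 7 events, so 6 events would fall outside it.

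A second reply is that 4.5.3 nowhere says point estimate, and that the interval in its 3% sentence may be meant to carry over to the 5% sentence. That is possible, but the text attaches the interval to one step and omits it from the next. Even if carried over, 4.5.3 would not say that the lower limit must exceed 5%, as 9.4 does.

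Three further limits stand. The absence of a time point in a general closure section is a weaker discrepancy than the threshold itself. Section 4.5.3 refers to one or both treatment modalities and 9.4 to the CEA and CAS arms, which are the same rates; whether stopping means one substudy or both is left open by both sections, so it is a shared ambiguity rather than a contradiction. And this cannot be called the only obligatory safety rule, because the DSMB section listed in the table of contents is not in the text available for review. Whatever it says, it cannot make 4.5.3 and 9.4 agree.

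**Conclusion.** The concern holds as an internal contradiction in a decision threshold. Under 4.5.3 the recommendation becomes obligatory when the rate exceeds 5%; under 9.4, only when the lower 80% limit does. With exact limits the gap is 6 against 8 to 9 events in 100 patients, 11 against 14 to 15 in 200, 21 against 25 to 27 in 400, and 41 against 47 to 50 in 818. The existence of the gap does not depend on the interval method; its size depends on the assumed method and number of patients. In the gap, the recommendation is obligatory under 4.5.3 and optional under 9.4.

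A reader might also infer that the protocol is deficient because it gives no trigger table or error rates for the rule. That is detail that an analysis plan or a DSMB charter commonly supplies, and its absence here is not part of the error.

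**What to change.** Reconcile sections 4.5.3 and 9.4 to one rule, worded identically in both places or stated once and cross-referenced. It should state:
- the quantity compared with 5%;
- the interval, if any: method, and whether 80% is two-sided or one-sided;
- the looks at which it applies: the three-year safety interim, the regular safety checks, or both;
- whether a trigger in one substudy affects that substudy alone or both.

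Which rule applies is for the sponsor and the DSMB to decide. The DSMB section should be checked against the agreed wording. The cost is two reworded paragraphs in an amendment, with no change to sample size or data collection. A short table of trigger counts in the DSMB charter would be a useful addition but is not needed to remove the contradiction.

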4.6 Prior and concomitant illnesses

Relevant additional illnesses present at the time of informed consent are regarded as concomitant illnesses and will be documented on the appropriate pages of the case report form (CRF). Included are conditions that are seasonal, cyclic, or intermittent (e.g. seasonal allergies; intermittent headache).

Patients with related stroke symptoms within the territory of the treated vessel within the last 180 days are not allowed to include into the trial.

Abnormalities which appear for the first time or worsen (intensity, frequency) during the trial are adverse events (AEs) and must be documented on the appropriate pages of the CRF.

4.7 Prior and concomitant treatments

Relevant additional treatments administered to the subjects on entry to the trial or at any time during the trial are regarded as concomitant treatments and must be documented on the appropriate pages of the CRF. There are medical or surgical treatments prohibited during the trial. If a major surgery is planned during the first 8 weeks after randomization patients should no be included prior this operation.

5 TRIAL PROCEDURES

5.1 Description of trial days

Study visits are scheduled as follows:

Screening

Randomization (Screening and randomization can be done on the same day, must be done within 14 days after screening)

Therapy [=day 0] (if randomized to CAS or CEA, must be within 28 days after randomization)

Day 1 \pm 0 after therapy (if randomized to CAS or CEA)

30 \pm 3 days after randomization (if randomized to BMT) resp. after therapy (if randomized to CAS or CEA)

6 months \pm 7 days after randomization

1 year \pm 14 days after randomization

2 years \pm 14 days after randomization

3 years \pm 28 days after randomization

4 years \pm 28 days after randomization

5 years \pm 28 days after randomization

An overview about the procedures to be done at specific visits can be found on page 9.

5.2 Screening and randomization

To qualify for this trial, patients must have met all above described inclusion and none of the exclusion criteria. Screening and randomization can be done at the same day, and randomization must be done within 14 days after screening, otherwise screening-examinations have to be repeated. The interventional therapy that will be tested vs. BMT has to be chosen by the treating physician and the patient prior to randomization. Following this decision patients will be assigned to SPACE2a or SPACE2b. Randomization between BMT and intervention is performed after the eligibility of a patient has been accepted by the involved discipline and after the patient has been examined from the study neurologist. Randomization will be done with an internet-based system provided by the data-center in Munich. Randomization will be stratified by an age-limit of 75years, providing the same numbers of instances per group in both age-cohorts. If the patient has been randomized to the interventional arm, treatment must be done within 4 weeks after randomization. Events occurring between randomization and treatment are counted within the allocated treatment group. Events between screening and randomization are not counted, but have to be noticed in preexisting condition in the CRF.

Before randomization following procedures has to be done:

5.2.1 Informed consent

The patient must be able to understand the nature of the trial and the related procedures and sign the informed consent form in person. Informed consent must be available before any study related procedures.

5.2.2 Risk factor screening

Blood pressure: Measured at both arms after 5 minutes rest

Diabetes: Measurement of fasting blood glucose and of the HbA1c

Lipids: Fasting Cholesterol including LDL and HDL, and triglycerides. The necessary blood samples will be taken as clinical routine and are not study specific.

Peripheral pulse status

Smoking history

Bodyweight, height, hip-waist-ratio

Assessment of physical activity measured as numbers of time-intervals of above 30minutes activity.

5.2.3 Neurological examination

Modified Rankin Score (mRS) and NIH-Stroke Scale (NIHSS) are determined at screening as the basis for the follow-up-examinations. A mRS > 1 at baseline is an exclusion criterion. All neurologists must have a NIHSS certificate (<http://asa.trainingcampus.net/uas/modules/trees/windex.aspx>).

5.2.4 Drug history

Relevant medication (e.g. antiplatelets, antihypertensives, lipid-lowering-drugs) will be documented with name and dosage and way of application at every visit. In case of an outcome event any medication will be documented.

5.2.5 Ultrasound examination

The ultrasound examination including color-coded extracranial Duplex and examination of the intracranial circulation must be done by a certified examiner (see Appendix). Documentation contains at least grading of the stenosis, Plaque morphology and a measurement of the Intima-Media-Thickness in the common carotid arteries.

Stenosis severity as measured with ultrasound is usually expressed following the method of the ECST. If a conversion from a NASCET measurement is necessary following equation will be used: $\%^{NASCET} = (\%^{ECST} - 43) \times (100 / 57)$ [11].

5.3 Treatment

5.3.1 Allocation to treatment

Eligibility of a patient will be determined by a Neurologist.

Old: Both surgeons and interventionalists need to confirm that treatment is feasible.

New: Surgeon or interventionalist need to confirm that treatment is feasible

BMT should start immediately after randomization; CEA or CAS must be performed within 4 weeks after randomization. In the case of a bilateral stenosis, randomization is performed for one side only, usually the side with the more severe stenosis.

Keeping a screening log is mandatory. The screening log should list all patients which are suitable for the trial but were not randomized and includes the reason (e.g. on of the Exclusion criteria) why the patients were not randomized and the method of treatment. The Steering Committee will look into this screening log and compare it to the sites surgical and interventional program. All centers are encouraged to include the majority of potential patients into the study.

5.3.2 Best medical treatment

All patients, also those individuals randomized for treatment with CEA or CAS, will be treated with up-to-date medication following national and international guidelines. Recommendations for this treatment will be given by the 'best medical treatment' subcommittee (see Appendix).

5.3.3 Carotid endarterectomy

Standards for surgical treatment are formulated by the 'vascular surgery' subcommittee (see Appendix)

5.3.4 Carotid artery stenting

Standards for endovascular treatment are formulated by the 'endovascular treatment' subcommittee (see Appendix)

5.4 Blinding

Due to the nature of the treatments involved, blinded treatment is not possible; with ultrasound it is clear to see how the patient is treated. Therefore the study has to follow an open design. However, to minimize a potential bias due to the open design, a physician, not directly involved in the CAS or CEA-procedure, is responsible for the follow-up examinations and end-point evaluation.

5.5 Follow-up examinations

The duration of the trial for each subject is 5 years. After the periprocedural phase yearly examinations are scheduled. Each visit consists of an event-screening, a risk-factor screening, and an ultrasound-examination.

The 30day visit for patients randomized into the BMT-arm is primarily used to evaluate if the recommendations for risk-factor-modification have been fulfilled.

Events are screened using a standardized questionnaire. An event has occurred if one of the following questions has been answered positively:

„Ist (seit der letzten Untersuchung) eine vorübergehende Sehstörung auf einem Auge aufgetreten?“

„Ist (seit der letzten Untersuchung) eine Schwäche oder Sensibilitätsstörung auf einer Körperseite aufgetreten?“

„Ist (seit der letzten Untersuchung) eine Sprachstörung aufgetreten?“

„Haben sich (seit der letzten Untersuchung) neue Beschwerden entwickelt?“

If a cerebrovascular outcome-event occurred an appropriate neuroimaging should be performed to distinct between possible types of stroke. In addition the mRS and NIHSS have to be assessed and documented. 30 days after symptom onset the patient has to be contacted to assess the mRS at this time point. In case of an ipsilateral cerebrovascular event in a subject randomized into the BMT-arm, patient should be considered for CEA or CAS following actual guidelines for treatment of symptomatic stenosis.

Risk-factor screening, assessment of medication, and ultrasound-examinations has to be done at any follow-up visit like described above (section 5.2)

5.6 Plan for treatment or care after the trial

Medical treatment with risk-factor modification will be continued after the end of the follow-up period (5 years in each individual). Responsible for control of these procedures will be the general practitioner of the patient.

6 ASSESMENTS

6.1 Definitions

Ischemic Stroke: New focal neurological deficit of vascular origin lasting more than 24 hours, absence of intracranial hemorrhage upon brain imaging.

Hemorrhagic Stroke: New focal neurological deficit of vascular origin lasting more than 24 hours, proof of intracranial hemorrhage upon brain imaging.

Ipsilateral stroke: Stroke within the territory of the treated carotid artery.

Disabling stroke: Stroke leading to a disability of at least 3 on the modified Rankin scale at day 30±3 after symptom onset.

Myocardial infarction: Detection of rise and/or fall of cardiac biomarkers (preferable troponin) with at least one value above the 99th percentile of the upper reference limit together with evidence of myocardial ischemia with at least one of the following [21]

- Symptoms of ischemia
- ECG changes indicative of new ischemia (new ST-T changes or new left bundle branch block (LBBB))
- New onset of pathological Q waves in ECG
- Imaging evidence of new loss of viable myocardium or new regional wall motion abnormality

Vascular death: Deaths due to stroke, myocardial infarction, or hemorrhage as well as any deaths those were not clearly non-vascular.

Technical failure: Inability to treat the stenosis with the allocated method or remaining stenoses of at least 70% following ultrasound-criteria at day 1.

Restenosis: Recurrent stenosis of at least 70% following ultrasound-criteria, which will be defined in the 'Neurology quality appendix'.

Observation period: 30 day endpoints for patients randomized into the BMT-group are evaluated after 30±3 days after randomization. 30 days risks for patients randomized into the CAS or CEA-arm are evaluated between randomization and 30±3 days after the procedure. Medium-term (up to 2 years) observational period's starts at the time of randomization, assessment can be done in a time period ±14 days around the calculated date. Long-term (up to 5 years) observational period's starts at the time of randomization, assessment can be done in a time period ±28 days around the calculated date.

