6.3 Evaluation of efficacy

6.3.1 Primary endpoint

The primary efficacy endpoint is the cumulative rate of any stroke (ischemic or haemorrhagic) or death from any cause within 30 days plus ipsilateral ischemic stroke within 5 years of follow up.

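### As written, a late ipsilateral ischemic stroke that kills within 24 hours does not meet the primary endpoint definition, and a stroke that is never imaged fits neither defined stroke type

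*Protocol*

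**What the plan says.** Section 6.1 defines two stroke types, each by a duration and an imaging result. The first reads: "Ischemic Stroke: New focal neurological deficit of vascular origin lasting more than 24 hours, absence of intracranial hemorrhage upon brain imaging". The second sets the same duration but asks for the opposite finding on the scan: "Hemorrhagic Stroke: New focal neurological deficit of vascular origin lasting more than 24 hours, proof of intracranial hemorrhage upon brain imaging".

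Stroke as such has no definition of its own. The ipsilateral qualifier adds only the territory: "Ipsilateral stroke: Stroke within the territory of the treated carotid artery".

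Section 6.3.1 then sets the primary efficacy endpoint in two parts. Up to day 30 it counts "any stroke (ischemic or haemorrhagic) or death from any cause within 30 days". From then on it counts only what follows: "plus ipsilateral ischemic stroke within 5 years of follow up". Death is not a component after day 30.

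On imaging, section 5.5 says: "If a cerebrovascular outcome-event occurred an appropriate neuroimaging should be performed to distinct between possible types of stroke". This is a recommendation, and the protocol sets no time limit for the scan.

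Section 6.1 also defines "Vascular death: Deaths due to stroke, myocardial infarction, or hemorrhage as well as any deaths those were not clearly non-vascular". Vascular death enters the long-term analysis only through a secondary endpoint in 6.3.2, which combines it with any stroke up to 5 years. Section 6.4 sends all suspected strokes and all deaths to a blinded committee for final classification.

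**The concern.** The usual reason for a 24-hour rule is to separate stroke from transient ischemic attack. Without an alternative for death, the rule also removes strokes whose deficit lasted less than 24 hours because the patient died. These are among the most severe events the trial is meant to prevent. A mild late stroke with a scan counts, while a late stroke fatal at 18 hours does not.

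This runs against section 2.3, which treats periprocedural complications together with later ipsilateral ischemia as the clinically relevant total. The imaging condition leaves a second, smaller gap: the protocol allows a stroke to go unscanned but has no class for it.

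At stake is the completeness of the primary endpoint in a trial with few events. Committee members applying 6.1 literally would have to exclude such cases, or else make up a rule case by case.

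**Working it through.** **1. Reading the definitions against the endpoint**

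| Ipsilateral event | Meets 6.1 ischemic stroke? | Counts under 6.3.1? |
|---|---|---|
| Infarct in year 3, deficit over 24 h, scan without hemorrhage | Yes | Yes |
| Infarct in year 3, scanned, fatal at 18 h | No (duration) | No; vascular death only |
| Stroke in year 3, survived, scanned late without hemorrhage | Yes (no time limit on the scan) | Yes |
| Stroke in year 3, never scanned | No (imaging) | No |
| Stroke by day 30, fatal at 18 h | No (duration) | Yes, as death from any cause |

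The gap therefore lies after day 30. It concerns rapidly fatal ischemic strokes and strokes never imaged. Late hemorrhagic stroke is outside the primary endpoint by design and is not part of this point.

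**2. Reproducing the plan's sample size**

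Inputs from section 9.1: BMT rate 0.01 per year, hazard ratio 0.50 (so 0.005 per year with intervention), two-sided 5%, power 80%, accrual 5 years plus follow-up 3 years. From section 4.1: 818 patients per arm.

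- Events needed (Schoenfeld, 1:1): (1.960 + 0.842)² / (0.25 × (ln 0.5)²) = 7.849 / 0.1201 = 65.3.
- Event probability with uniform accrual: 1 − (e^(−3λ) − e^(−8λ)) / (5λ). This gives 0.0534 for BMT and 0.0271 for intervention, mean 0.0403.
- Total N = 65.3 / 0.0403 ≈ 1,623 (unrounded inputs).

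This agrees with the stated 1,624 without an interim analysis and is within 1% of the 1,636 with one. (The protocol attaches 3 years of accrual and 5 of follow-up to the 1,624. That layout gives about 1,378, which is a separate matter.)

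**3. Expected events per substudy**

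- 5 + 3 layout: 818 × 0.05342 = 43.7 and 818 × 0.0271 = 22.2, total 65.9.
- Exactly 5 years per patient: 818 × (1 − e^(−0.05)) = 39.9 and 818 × (1 − e^(−0.025)) = 20.2, total 60.1.

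**4. Size of the loss**

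The protocol gives no share of strokes fatal within 24 hours or never imaged. As an assumption, take 1% to 3% for the first and 2% to 8% for the second, together 3% to 11%. The sum is generous: it counts twice any patient who dies early without a scan, and it applies the loss to all events, although deaths up to day 30 count in any case.

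- Events lost: 2.0 to 7.2 of 65.9, or 1.8 to 6.6 of 60.1.
- Power = Φ(√(E/4) × ln 2 − 1.960), with the hazard ratio held at 0.50.

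| Loss | Events left (of 65.9) | Power | Events left (of 60.1) | Power |
|---|---|---|---|---|
| 0% | 65.9 | 80.3% | 60.1 | 76.6% |
| 3% | 63.9 | 79.1% | 58.3 | 75.4% |
| 11% | 58.6 | 75.6% | 53.5 | 71.7% |

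On either event count the loss costs about 1 to 5 points of power.

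**The case against.** The strongest reply is adjudication. Section 6.4 sends every suspected stroke and every death to a blinded committee that makes the final classification, so a stroke fatal at 18 hours does reach expert review. Section 10.3, which describes the committee, and the Neurology standard procedures are not in the text examined here, and either may hold a rule for such cases. This stands as a limit on the claim: what is shown is that the written definition excludes these events, not that they will be lost. It does not remove the point, because 6.4 states no exception to 6.1.

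Second, requiring a scan before an event is called ischemic is a defensible choice for specificity in an open trial. Counting unscanned strokes as ischemic by default would exchange missed events for misclassified ones. This stands, and is why that counting belongs in a sensitivity analysis.

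Third, late fatal strokes are still captured by the secondary endpoint of any stroke or vascular death. This is true, but it does not repair the primary endpoint.

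Two stronger readings are tempting and should not be drawn:

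- A reader might infer that the 30-day safety rate also loses unscanned strokes. Sections 2.2, 6.2 and 9.2 use any stroke without a qualifier. Only 6.3.1 adds the two types in brackets, which can naturally be read as including both. Fatal strokes in that window count as deaths.
- A reader might infer that closer watching of CEA and CAS patients makes the loss unequal between arms. From day 30 the visit schedule is the same in both arms (5.1 and the visit plan); the only extra visit is day 1 after the procedure. Section 2.3 does expect late events mainly under BMT, so losing only late events could dilute the contrast. The protocol does not separate the periprocedural risk from the intervention-arm rate, so the size of any such effect cannot be established from it.

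**Conclusion.** The point holds as a defect of wording in the primary endpoint. Under 6.1 and 6.3.1 as written, a late ipsilateral ischemic stroke fatal within 24 hours is not a primary event even when imaged, and a stroke never imaged belongs to neither defined type. Both statements are subject to any rule in section 10.3 or the committee's procedures.

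The effect is probably small: a few events per substudy. The power figures rest on three assumptions: the 3% to 11% loss, which is not in the protocol; equal proportional loss in both arms; and a hazard ratio unchanged at 0.50. They show the scale and are not an estimate. The reason to act is that the definition leaves out severe events that the endpoint is meant to include, and that correcting it costs little.

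**What to change.** In section 6.1:

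- Define both stroke types as a new focal deficit of vascular origin *lasting more than 24 hours or leading to death*, and keep the imaging criterion that separates them.
- Add a category *stroke of undetermined type (no imaging)* and state that it counts as any stroke.

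In the analysis, report a sensitivity analysis of the primary endpoint that counts ipsilateral strokes of undetermined type as ischemic. The primary analysis keeps imaging as the condition for ischemic stroke. If the endpoint committee already has rules for these cases, refer to them in 6.1 and bring the two texts into line.

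The cost is the wording in 6.1, one more category on the outcome event form, and slightly more adjudication and analysis work. An occasional unscanned hemorrhage will be counted as ischemic in the sensitivity analysis, but not in the primary analysis. No treatment or visit changes.
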